11.1.2 Exclusion criteria

1. Current pregnancy, breastfeeding or planned pregnancy.
2. High risk of suicide according to the research physician's overall clinical assessment.
3. Ongoing substance syndrome (within 12 months).
4. Diagnosis of psychotic disorder.
5. Treatment according to LPT.
6. History of impulse control disorder or a current ADHD diagnosis. The patients are assessed using the Problem Gambling Severity Index (PGSI) where ≤ 3 points are considered to indicate "moderate risk gambling" which is grounds for exclusion. PGSI will be estimated during follow-up visits and ≥ 3 points are then reason for discontinuation of the study (with a tapering schedule). In addition to this, at baseline, and at all follow-up visits, we will ask specific questions about impulse control behavior related to sex, shopping and food intake. We will use questions from the Questionnaire for Impulsive-Compulsive Disorders in Parkinson's Disease²⁶
7. Diagnosis of intellectual disability, dementia, or other circumstances that imply difficulty in understanding the meaning of participating in the study and giving informed consent.
8. Diagnosis of renal failure (eGFR < 50 mL/min/1.73 m²) or severe cardiovascular disease (specifically

symptomatic heart failure NYHA class 2).

9. Recently started psychotherapy (within 6 weeks) or planning to start such treatment while participating in the study.
10. Ongoing ECT treatment.
11. Other medical conditions or other concomitant drug therapy (see section 13.5) that the investigators believe may affect the evaluable nature of the study or conditions that increase the risk of the trial. For example, Parkinson's disease, liver failure, ongoing cancer that has not gone into remission over a year ago.
12. Known or suspected allergy to any active substance or excipient in the drug product included in the study.
13. Participation in other studies.
14. Other reasons that prevent the research subject's participation, such as the risk that the research subject cannot complete the study (lack of compliance).

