11 STUDY POPULATION

Fifteen research subjects with either unipolar depression, bipolar disorder in depressive phase, or dysthymia are recruited to receive pramipexole treatment. All research subjects are asked to participate in the substudy (fMRI examination). Patients from the outpatient clinics and inpatient wards at the psychiatry in Lund will be asked if they want to participate in the study by treating physicians. Only those who are cared for under the Health and Medical Services Act (i.e. not under compulsory care) may be considered for the study. After the patient has been informed of the study and given consent, the patient will be invited to *screening* visits to the doctor responsible for research at the research clinic or the research physician visits the patient in the ward where the patient is admitted. All examinations/visits in connection with the study will take place at the adult psychiatry in Lund, while the fMRI examination will take place at Skåne University Hospital in Lund.

Research subjects who meet all inclusion criteria and no exclusion criteria as set out below, may be included in this study.

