11.2 CRITERIA FOR DISCONTINUATION OF STUDY PARTICIPATION

1. Low compliance
2. New acute suicidality
3. Deterioration by more than 25% on MADRS
4. In case of unacceptable side effects such as the development of manic state, impulse control disorder, or symptoms of heart failure
5. Pregnancy
6. The research subject may terminate his/her participation in the study at any time without incurring any consequences for his/her further treatment.

Investigators may at any time discontinue a research subject's participation in the study due to, for example, unacceptable side effects, deteriorating mental health status, or non-compliance with the procedures in the study protocol (see study adherence section 12.8).

If research subjects discontinue prematurely, a plan will be drawn up for the discontinuation of pramipexole (tapering schedule). This is done according to recommendations in FASS but can be adapted individually if needed (e.g. withdrawal side effects that lead to slower joint progression).

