27 AMENDMENTS

No	Date	Change and cause	Author and new version
1	190617	Based on comments from Ethics committee (and because pramipexole can cause impulsive disorders e.g. increased gambling as a side-effect), we changed the protocol and added to the exclusion criteria nr 6 a new scale "Problem Gambling Severity Index"; to ensure the exclusion of subject with risk gambling. The rating takes place at baseline meetings and during every second week during the pramipexole treatment.	[name] v1.1

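### The PGSI cut-off in exclusion criterion 6 is reversed: as written it bars low scorers and admits only scores that already meet the follow-up stopping rule

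*Combined protocol and SAP*

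**What the plan says.** Section 11.1.2, criterion 6, excludes people with a history of impulse control disorder or a current ADHD diagnosis, and then adds a numeric gate based on the PGSI. The gate reads "PGSI) where ≤ 3 points are considered to indicate" moderate-risk gambling, and that range is a reason not to enrol. The sentence after it sets the on-treatment rule: "PGSI will be estimated during follow-up visits and ≥ 3 points are then reason for discontinuation of the study", with tapering.

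Section 27, amendment 1, records that the scale was added after comments from the ethics committee, "because pramipexole can cause impulsive disorders e.g. increased gambling as a side-effect", and that the aim was "to ensure the exclusion of subject with risk gambling".

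Section 11 makes the exclusion list binding: "Research subjects who meet all inclusion criteria and no exclusion criteria as set out below, may be included in this study". The schedule in section 12 places PGSI at screening, baseline, V2, V4, V6, V8 and the week 10 visit.

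**The concern.** The two sentences of criterion 6 use the same scale and nearly the same number with opposite signs. At entry a low score is the problem; at follow-up a high score is. Both cannot describe gambling risk. The label attached to the entry range also fails, because a person scoring 0 would count as a moderate-risk gambler.

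The criterion is a safety gate. Section 13.1 lists behavioural symptoms of disturbed impulse control among the common reactions to pramipexole (at least 1 in 100, fewer than 1 in 10). Section 13.3 requires the drug to be tapered off, not merely reduced in dose, if impulse control disorder appears. Section 8 plans no external safety committee, so protection rests on the eligibility rules and the visit-level rules. Applied literally, the gate would turn away people with no gambling problem and let those with the highest scores start the drug.

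**Working it through.** No sample size, power or error rate is involved. The check is on which scores each rule lets through.

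**Inputs**
- Entry rule as written (section 11.1.2, criterion 6): excluded if PGSI ≤ 3.
- Follow-up rule (same criterion): discontinued if PGSI ≥ 3.
- Eligibility (section 11): a candidate must meet no exclusion criterion.
- Assumption: scores are whole numbers starting at 0. The documents do not give the maximum, so it is set to 9 and then to 27.

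**Direction of the scale, from the documents alone**

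| Text | Which scores it treats as risky |
|---|---|
| Follow-up rule, criterion 6 | high (3 or more) |
| Amendment 1, purpose | whatever range counts as risk gambling is to be excluded |
| Entry rule, criterion 6 | low (3 or less) |

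The follow-up rule fixes the direction: higher means worse. Given that, the purpose in amendment 1 requires high scores to be excluded at entry, and the entry rule is the odd one out. The conflict does not depend on the amendment log, since it already stands between two adjacent sentences of the current text.

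**Rule as written**
- Not excluded: PGSI > 3, that is {4, 5, …}.
- Not discontinued: PGSI < 3, that is {0, 1, 2}.
- Scores in both sets: none.
- Admitted scores that meet the stopping rule if unchanged: 6 of 6 (scores 4 to 9) with a maximum of 9; 24 of 24 (scores 4 to 27) with a maximum of 27.
- Smallest fall needed to stay in: the lowest admitted score is 4 and the highest score allowed to continue is 2, so 4 − 2 = 2 points. Higher entry scores need larger falls.
- First occasion on which this applies: the V2 rating.

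**Rule with the sign corrected (excluded if PGSI ≥ 3)**
- Admitted: {0, 1, 2}.
- Admitted scores that already meet the stopping rule: 0 of 3.
- A score of exactly 3 is excluded at entry and leads to discontinuation at follow-up, so the two rules agree.

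**Is the right cut-off given elsewhere?** Section 11.2 lists impulse control disorder as a reason to stop but gives no PGSI number. The synopsis names impulse control disorder without a score. Section 17.2 does not list the PGSI among the scales appended to the CRF. Criterion 6 is the only place with an entry threshold.

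**The case against.** The strongest reply is that this is an obvious slip of one symbol. The label, the next sentence and the amendment all point to 3 or more, so a reader can recover the intended rule from the paragraph. In a single-centre pilot of fifteen patients, it is hard to imagine staff refusing every non-gambler. That is probably right as a description of practice. It does not repair the governing text, under which enrolling a patient who scores 0 is an eligibility deviation.

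Other safeguards also exist. Criterion 6 separately excludes a history of impulse control disorder, and criterion 11 covers conditions that raise the risk of the trial. During treatment the stopping rule is correctly written, and section 11.2 adds "In case of unacceptable side effects such as the development of manic state, impulse control disorder, or symptoms of heart failure". Questions about sex, shopping and food intake are asked at baseline and at every follow-up visit. These points stand, and they narrow the exposure: a known gambling disorder is barred whatever the PGSI sign, and harm that develops on treatment is still caught. What remains uncovered is the undiagnosed risk gambler at screening, for whom the scale was added.

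It is also fair to say that nothing in the primary analysis depends on this criterion. The sample size, the analysis sets and the paired t-test are unaffected.

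A misread symbol in the PDF cannot be ruled out entirely, but the ≥ sign was read correctly in the very next sentence, and both signs appear correctly in the age criterion.

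**Conclusion.** The point holds. Criterion 6 is wrong as written: it excludes PGSI 0 to 3, admits only 4 and above, and leaves no score that both permits entry and permits continuation without a fall of at least 2 points. The finding rests on the literal text and on whole-number scores; it does not depend on the maximum of the scale. The claim that the trial could not run is a consequence of literal application, not a prediction of what the site would do. Because this is a decision threshold in a safety criterion, and no other section supplies the correct value, it must be fixed even though the cause is almost certainly typographical.

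**What to change.** Change the entry inequality in criterion 6 to PGSI ≥ 3, so that the range labelled as risk gambling is the range excluded. No separate provision is needed for a score of exactly 3, because the corrected sign treats it the same way at both stages. Check that the CRF eligibility checklist, which is not among the documents, carries the corrected rule, and check that PGSI scores already collected were judged against 3 or more.

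The text edit is one symbol. Section 20.1 gives a change to an exclusion criterion as an example of a significant change, so a short formal amendment may be needed. There is no effect on sample size, visit schedule or analysis.

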13 STUDY DRUG

13.1 INVESTIGATIONAL MEDICINAL PRODUCTS

In the study, the investigational medicine contains the active substance pramipexole. In Sweden, it was previously marketed under the name Sifrol but is now available in several generic versions. The dosage of pramipexole can be stated either as a base or as salt. In FASS, it is first and foremost the dosage as a base that is stated and the corresponding concentration in salt is given in parentheses. This protocol specifies dosage in salt form to be consistent with dosage indicated in the literature and abroad. In the diary and patient information for study participants, the dose is stated in base, as is stated on the medicine package and in the FASS.

Pramipexole is approved in the EU and is indicated as a symptomatic treatment of idiopathic Parkinson's disease, alone (without levodopa) or in combination with levodopa, in the maximum dose of 4.5 mg of salt. Pramipexole is also indicated as a symptomatic treatment of moderately to severely idiopathic restless legs syndrome in doses up to 0.75 mg of salt. Both apply to adults and not to children.

Pramipexole has a purely antidepressant effect (in addition to the effect on the underlying disease) in patients with Parkinson's disease, according to clinical studies. It has also been shown to reduce anhedonia symptoms in these patients³⁷. However, pramipexole has no approved indication for the treatment of mood disorders. In this study, the research subjects will reach a maximum dose of 4.5 mg of salt/day that is already approved for the treatment of Parkinson's disease.

Common Side Effects According to FASS (Indication Parkinson's Disease):

Very common (≥ 1/10): Somnolence, Dizziness, Dyskinesia and nausea.

Common (≥ 1/100, < 1/10): Insomnia, Hallucinations, Abnormal dreams, Confusion, Behavioral symptoms of disturbed impulse control and compulsive behavior, Headache, Visual impairment incl. diplopia, blurred vision and impaired visual acuity, Hypotension, Constipation, Vomiting, Fatigue, Peripheral oedema, Weight loss incl. decreased appetite.

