16.3 STATISTICAL ANALYSIS OF PRIMARY, SECONDARY AND EXPLORATORY VARIABLES

All statistical analysis is performed using the IBM SPSS Statistics v24 software. Paired T-test (2-tailed) is used to analyze the difference in DARS scores between *baseline* and after ten weeks of treatment with pramipexole (primary variable). Normal distribution is expected based on previous studies. Descriptive analysis is performed by response (reduction by at least 50% in MADRS score), remission (MADRS ≤ 10 at study end) of depression symptoms (secondary variable), and number of *dropouts*. Descriptive analysis, mean and *range*, is performed on the dosage of pramipexole at the end of the visit. Of the exploratory variables, similar *paired* T-tests (or equivalent non-parametric method if necessary) are used for the analysis of difference in total scores MADRS, SHAPS, MAP-SR, AES, GAD-7, Fatigue Severity Scale and Insomnia Severity Index.

Analyses may also be made on imputed datasets. If values are missing from the measurements over time, they will be replaced with the means of adjacent values before and after the missing value or with the last observation.

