17.2 CASE REPORT FORM (CRF, DATA COLLECTION DOCUMENTS)

The data collected in the study will be recorded in a case *recordform* (CRF) in paper form that is prepared specifically for recording data for the study in question. A research person form must be available for each research subject and all questions in the research person form must be answered. Questions that cannot be answered will be noted with ND=Not done, NA=Not applicable or NK=Not known. Any corrections are made by crossing out the incorrect and dating and signing the change and writing the correct information next to it.

The following rating scales will be added as an appendix to the CRF: MINI, SUAS, SHAPS, MAP-SR, AES, GAD-7, *Insomnia Severity Index*, and *Fatigue Severity Scale*.

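### The impulse-control questions promised for every follow-up visit have no row in the visit table and no planned summary, so new behaviours not raised as incidents could drop out of the tolerability result

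*Combined protocol and SAP*

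**What the plan says.** Criterion 6 in section 11.1.2 contains two follow-up assessments as well as an entry condition.

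- **Gambling.** PGSI is scored at entry and again at follow-up, where "≥ 3 points are then reason for discontinuation of the study".
- **Sex, shopping and food intake.** At baseline and "at all follow-up visits, we will ask specific questions about impulse control behavior related to sex, shopping and food intake". The source is given as "We will use questions from the Questionnaire for Impulsive-Compulsive Disorders in Parkinson's Disease". No items, score or cut-off are named.

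Section 11.2 lists unacceptable side effects that end participation, "such as the development of manic state, impulse control disorder, or symptoms of heart failure". Section 13.3 repeats this as an exception to the usual step-down strategy and gives compulsive buying as one example. Section 13.1 places "Behavioral symptoms of disturbed impulse control and compulsive behavior" in the common class (at least 1/100, below 1/10) for the Parkinson's indication.

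The section 12 table has a PGSI row marked at screening, baseline, V2/V4/V6/V8 and v10. It has no row for the other questions. Section 17.2 states: "The following rating scales will be added as an appendix to the CRF: MINI, SUAS, SHAPS, MAP-SR, AES, GAD-7", followed by the insomnia and fatigue scales. In section 16.3, paired tests "are used for the analysis of difference in total scores MADRS, SHAPS, MAP-SR, AES, GAD-7, Fatigue Severity Scale and Insomnia Severity Index". The rest of that section covers DARS, response, remission, dropouts, final dose and imputation.

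**The concern.** A follow-up safety assessment that is stated only inside an exclusion criterion is easy to miss once a participant has been enrolled. At later visits, staff will normally work from the visit table and the procedure sections, and neither contains these questions.

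Tolerability of high-dose treatment is a stated question in the synopsis. Section 9.3 also defines the useful dose range partly by the absence of intolerable side effects. If the questions are skipped, or are asked but not tabulated, a report of no impulse-control problems could mean that none occurred, that nobody asked, or that nobody counted. With 15 participants and no control group, one overlooked case is a visible part of the result: 1/15 = 6.7%.

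**Working it through.** **Where each assessment appears**

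| Place | PGSI (gambling) | Sex, shopping, food questions | YMRS (mania), for comparison |
|---|---|---|---|
| 11.1.2, criterion 6 | yes | yes | no |
| 12, visit table | yes | no | yes |
| 12.3, baseline procedures | no | no | yes |
| 12.5 and 12.6, treatment and final visit | no | no | no |
| 13.3, dosage | no | no (compulsive buying named only as a stopping event) | yes, with weeks listed |
| 14.2.3, tolerability | no | no | no |
| 16.3, analysis | no | no | no |
| 17.2, list of appended scales | no | no | no |

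Mania and impulse control disorder share the same discontinuation rule. Mania has a scheduled scale in both the table and section 13.3. Gambling has one in the table. The other three behaviours have neither, and criterion 6 is the only place where the questions occur. The silence of 12.5 and 12.6 alone would prove little, since those sections also leave out most scheduled scales. What matters is that the table does not make up for it.

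**Which visits count.** The table's visit header covers physical visits (v2, v4, v6, v8, v10: 5), telephone weeks (v1, v3, v5, v7, v9: 5) and the tapering contact (v14: 1). The promise of all follow-up visits therefore means 5 occasions or as many as 5 + 5 + 1 = 11.

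**PGSI levels.** As printed, criterion 6 excludes at 3 points or fewer and discontinues at 3 points or more. Read literally, anyone admitted scores above 3 and already meets the follow-up rule. The two statements cannot both stand.

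**Scale.** The plan gives no figure to reproduce. Inputs: n = 15 treated and at least 10 completers (16.1); true rate p from the common class in 13.1, 1% up to an excluded 10%, with 5% added as an intermediate assumption. The chance of at least one case is 1 − (1 − p)^n.

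| p | n = 15 | n = 10 |
|---|---|---|
| 1% | 1 − 0.99^15 = 14.0% | 1 − 0.99^10 = 9.6% |
| 5% | 1 − 0.95^15 = 53.7% | 1 − 0.95^10 = 40.1% |
| 10% (limit) | 1 − 0.90^15 = 79.4% | 1 − 0.90^10 = 65.1% |

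If no case is seen, the one-sided 95% upper bound is 1 − 0.05^(1/n): 18.1% for n = 15 and 25.9% for n = 10. Even a complete record with no cases leaves a wide bound, and that bound is valid only if every participant was asked.

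**The case against.** The case on the other side limits the point in several ways, and most of it stands.

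- **Incidents are collected and reported.** Section 15.5 has a general question at each weekly contact, and sections 15.5 and 15.7.1 record incidents in the CRF and carry them to the final report. A reader might infer that milder changes go unreported. The documents do not support that: a change recorded as an incident is reported whether or not treatment stops. Nor do the sex, shopping and food questions have a numeric level for a change to fall below; the only such level is PGSI's. What remains is that the weekly question is open, and criterion 6 itself adds specific questions to it.
- **The CRF list is weak evidence.** A reader might infer from 17.2 that the answers cannot reach the data file. But that list also omits DARS (the primary variable), MADRS and YMRS, and 17.1 transfers relevant medical-record data to the CRF. The list is incomplete in general. DARS and MADRS, however, are backed by the table and 16.3, and YMRS by the table and 13.3.
- **Never asked would be too strong.** Criterion 6 is a current instruction in a single-centre study, and the table marks eligibility review at baseline. The exposed part is follow-up.
- **Stopped cases leave some trace.** Someone withdrawn for impulse control disorder counts as a dropout in 16.3, although no summary by reason is planned.
- **The amendment concerns gambling.** The log in section 27 describes adding PGSI. It does not show that an amendment about the other behaviours failed.
- **The frequency range is not the size of the gap.** A reader might take 14% to 79% as the chance of missing a case. It is the chance of any case, gambling included, at a Parkinson's rate. Section 8 considers the risk lower with shorter treatment and prolonged-release tablets, and criterion 6 excludes people with a history of impulse control disorder.
- **The analysis gap is wider.** Section 16.3 plans no incident or YMRS summary either, although adverse events are a secondary variable in the synopsis.

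None of this gives the questions a scheduled follow-up visit or a planned summary.

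**Conclusion.** The point holds as an internal inconsistency with a practical consequence. A follow-up assessment required by criterion 6 is absent from the visit table and the visit procedures, and neither it nor PGSI is summarised in 16.3. At follow-up, staff could omit it without departing from the table, and behaviours not volunteered or not judged to be incidents would be missing from the tolerability result.

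The chance of a missed case cannot be calculated from the documents, because it depends on how often the questions would be skipped and how often the open question would elicit the behaviour. The 14% to 79% range only indicates that at least one case among 15 is plausible if the Parkinson's class carries over; the true figure may be lower. The conclusion also assumes that staff follow the table at follow-up visits. No efficacy result or sample-size figure is affected.

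**What to change.** 1. **Section 12 table.** Add a row for the criterion 6 questions at baseline and at the follow-up visits. Name the questionnaire items used, and state whether telephone contacts and v14 count. Add a matching line to 12.3, 12.5 and 12.6.
2. **Section 17.2.** Include the questions and PGSI among the CRF forms, and complete the list for DARS, MADRS and YMRS at the same time. Because 17.2 requires unanswered questions to be marked as not done, not applicable or not known, a form would also separate a negative answer from a question not asked.
3. **Section 16.3.** Add a descriptive summary over all post-baseline visits: the number of treated participants with impulse-control behaviour new since baseline, by domain, together with PGSI scores, impulse-control incidents and the dose at onset. Count participants across all visits rather than comparing v10 with baseline, because affected participants may be withdrawn before v10.
4. **Criterion 6.** Reconcile the PGSI levels printed for exclusion and for discontinuation. Which is intended is for the sponsor and investigator to settle.

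The cost is one table row, one CRF page, a few sentences in the procedure sections and 16.3, and a slightly longer visit form. At the physical visits nothing is added beyond what criterion 6 already promises.
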